PGC-1a measurements. Blood samples will be collected in the morning, after an overnight fast and withholding all morning medications. Samples will be obtained at baseline and at the monthly visits throughout the trial. PGC-1a RNA and protein from peripheral blood mononuclear cells (PMBC's) will be measured by qRT-PCR and enzyme-linked immunosorbent assay (ELISA) respectively. RTPCR will be performed by the ABI PRISM 7900HT Sequence Detection System (Applied Biosystems, Foster City, CA). Each 25µl reaction consists of PGC-1a specific primers (Hs01016719_m1), cDNA template and qPCR gene expression Mastermix (Life technologies). Cycle threshold values for each reaction are adjusted automatically, and the fold changes are determined. The fold-changes values are derived relative to control and are represented as means + SEMs of mRNA expression normalized to β -actin and comparison made using ANOVA PGC-1a protein expression will also be performed using a PGC-1a ELISA kit (USA biological) as per the instructions of the manufacturer.

Adverse Events. We will monitor for known side effects of fenofibrate including, but not limited to,

myalgia, elevated blood pressure, and specifically alterations in hepatic or renal function, and photosensitivity using a questionnaire specifically designed for this purpose, blood pressure readings, and blood tests of renal and hepatic function at every monthly visit. In accordance with the recommendation in the package insert for fenofibrate, serum level of HDL-C will be assesses at Baseline Visit, week 12 and week 24. There are no contraindications for concurrent statin and fenofibrate use, but idiopathic myopathy and myositis are more common among patients treated with both agents. Fenofibrate is the only fibrate that does not appear to produce a substantial pharmacokinetic effect on statin elimination. Subjects can withdraw for any reason at any time.

5. List up to ten relevant references/articles to support the rationale for the research. Do not append an extensive NIH-grant-style bibliography.

REFERENCES

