Potential participants will be recruited from the UCI HD clinic where the study will be described to potential subjects. If the candidate is interested in participating, informed consent and Health Insurance Portability and Accountability Act of 1996 (HIPPA) authorization will be obtained. After consent, potential participants will be scheduled for the Screening Visit.

			1-	2-	3-	4-	5-	6-
	Screeni	Baselin	mont	mont	mont	mont	mont	mont
	ng Visit	e Visit	h	h	h	h	h	h
			visit	visit	visit	visit	visit	visit
Consenting	Х							
Review								
Inclusion/Exclusi	Х	X						
on Criteria								
Demographics								
and family and	Х							
medical history								
Vital signs	Х	Х	Х	Х	Х	Х	Х	Х
Renal and								
hepatic blood	Х	X	Х	Х	Х	Х	Х	Х
tests								
Concomitant								
medication	Х	X	Х	Х	Х	Х	Х	Х
review								
PGC1- α levels	Х	Х	Х	Х	Х	Х	Х	Х
Fenofibrate		v	v	Y	Y	Y	Y	Y
levels			^	~			~	~
Motor,								
Cognitive,								
Psychiatric,	Х	X			Х			Х
Functional								
measures								

Table 1.Study Schema

Clinical neurological and physical examination	х	х			x			x
Study drug reconciliation and dispensing		х	х	х	х	х	х	х
Adverse events questionnaire			Х	Х	Х	Х	Х	Х

Procedures: The trial will last 6-months and will require eight study visits: A Screening Visit and Baseline Visit prior to drug and a monthly visit for the 6-month trial (**Table 1. Study Schema below**). All visits will include: a fasting blood draw for leukocyte PGC-1α protein and transcript levels, and plasma fenofibrate levels; medication and medical history update; adverse events questionnaire; study drug accounting and distribution. The Baseline 3-month, and final 6-month study visit will include administration of the UHDRS, MoCA, and CGI (**Table 2. Study Outcomes**). Participants will be provided food and drink following the blood draw and before any clinical examinations and cognitive testing.

Screening Visit.

The following procedures will be performed at the Screening Visit (Visit SC):

- Obtain written informed consent (if not already obtained)
- Subject Number assigned
- Inclusion/exclusion criteria review
- Demographics
- Medical history
- Review concomitant and prior drug usage
- Obtain vital sign measurements
- Conduct general physical exam
- Conduct general neurological exam
- UHDRS Total Functional Capacity (TFC)
- Blood specimen collection for safety laboratory tests, including BUN, creatinine, ALT, AST, hematology, and serum pregnancy test for women of childbearing potential.

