- For women of childbearing potential, review of acceptable birth control methods that must be used during the study

All potential participants who meet the eligibility criteria after this screening will be scheduled for the Baseline visit within 14 days.

Baseline Visit.

The following baseline visit procedures will be performed within 14 days from the screening visit:

- Conduct final review of eligibility (prior to first dose). Subjects must continue to meet all inclusion and exclusion criteria at the Baseline Visit.
- Obtain vital sign measurements
- Complete all sections of the UHDRS (Motor, Cognitive, Behavioral, Functional, Independence, and TFC).
- Assess predominant HD symptoms (must be completed by the site investigator)
- Complete Neuropsychological Tests (Hopkins Verbal Learning Test-Revised, Symbol Digit Modalities Test, UHDRS Cognitive, Stroop Word and Benton Judgment of Line Orientation)
- Review concomitant drug usage
- Assess adverse events
- Instruct subject about correct administration of study drug
- Provide instructions to subject and caregiver (if applicable) on study drug consumption, compliance, and reporting of adverse experiences

This visit should take about 2-3 hours.

Following phlebotomy subjects will receive calories and fluids (e.g., energy bar and juice) and then undergo clinical evaluations, including UHDRS, cognitive tests, and CGI-S. Upon conclusion of clinical evaluations the study procedures will be reviewed with the subject and the one month supply of study medication will be provided.

Monthly Visits. The 6, monthly visits will involve a fasting blood draw, a brief clinical examination and completion of an adverse events questionnaire. A pill count will be done to monitor study drug compliance. Monthly visits are expected to last 30 minutes to one hour. The 3- and 6-month visits will include administration of the UHDRS, MoCA, Neuropsychological exams and the CGI.

Randomization. The first 20 participants eligible for the trial after screening will be randomly assigned to either the active drug or placebo group at a 3:1 ratio. Enrollment ID Numbers will be developed by the study statistician and will correspond to specific study drug vials. Study drug will be labeled with a four-digit Enrollment ID Number assigned to that subject.

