Study drug reconciliation and distribution		X	х	Х	Х	Х	X	Х
Adverse events questionnaire			X	X	X	X	X	Х

Procedures: The trial will last 6-months and will require eight study visits: A Screening Visit and Baseline Visit prior to drug and a monthly visit for the 6-month trial (**Table 1. Study Schema**). All visits will include: a fasting blood draw for leukocyte PGC-1 α protein and transcript levels, and plasma fenofibrate levels; medication and medical history update; adverse events questionnaire; study drug accounting and distribution. The Baseline 3-month, and final 6-month study visit will include administration of the UHDRS, MoCA, Neurosychological exams and CGI (**Table 2. Study Outcomes**). Participants will be provided a meal following the blood draw and before any cognitive testing.

Screening Visit. Potential participants will be recruited from the UCI HD clinic where the study will be described and if interested, informed consent and Health Insurance Portability and Accountability Act of 1996 (HIPPA) authorization will be obtained. After consent, potential participants will be scheduled for the first study visit where they will provide medical history, family history, and current medication information. All potential participants will arrive to this morning visit fasting and having withheld all medications from the previous evening. Total Function Capacity (TFC) score will be obtained. General and neurological exams will be conducted. Subjects with a TFC score blow 7 will be excluded. We will collect a blood sample for CBC w/diff, ALT, AST, BUN, creatinine and HDL-C. From the blood work, we will exclude potential participants with evidence of significant hepatic (transaminases >2 × upper limit of normal) renal dysfunction (serum creatinine > 2.0 mg/dl), or HDL-C below normal range (42). Any other

significant abnormality in the blood work that in the judgment of the Study Medical Director would affect participation in the clinical trial would also be considered. All potential participants who meet the eligibility criteria after this screening will be considered eligible for the clinical trial.

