Baseline Visit. The baseline visit will be completed within 14 days of the Screening Visit and prior to the administration of any study medication. We will collect a fasting blood sample for baseline leukocyte PGC-1 α protein and transcript levels. We will administer the full UHDRS and neuropsychological tests. In addition, the study procedures will be reviewed and a 1-month supply of study medication will be distributed.

Monthly Visits. The 6, monthly visits will involve a fasting blood draw, and query regarding adverse events by the investigators. A pill count will be done to monitor study drug compliance. Monthly visits are expected to last 30 minutes to one hour. The 3- and 6-month visits will include administration of the UHDRS, MoCA, Neuropsychological exams and the CGI.

Randomization. The first 20 participants eligible for the trial after screening will be randomly assigned to either the active drug or placebo group at a 3:1 ratio. We will allow patients using statins to enroll in the study because recent guidelines from the American College of Cardiology and the American Heart Association now recommend the use of these drugs in adults as primary preventative therapy for heart disease.

Blinding. The randomization assignment for each participant will be blinded to all clinical investigators and known only to the study statistician who will perform the randomization and maintain the randomization key. Group assignment will be un-blinded after the clinical trial is complete, or if there is a medical emergency for the participant which requires this.

2. Describe the duration of a subject's participation in the study. If there are sub-studies, include duration of participation in each sub-study.

Subject's participation will include a Screening and Baseline Visit as well as six (6) monthly follow-up visits. Total time for participant's participation is approximately 10 hours over a 7 month period.

3. List data collection instruments (e.g., measures, questionnaires, interview questions, observational tool, etc.).

Investigator-authored, non-standardized, or un-validated measures must be submitted for review.

-Demographics

- -Medical History
- -Unified Huntington Disease Rating Scale (UHDRS) Motor
- -Unified Huntington Disease Rating Scale (UHDRS) Behavioral
- -Montreal Cognitive Assessment (MoCA)
- -Clinical Global Impression (CGI)
- -Neurological examination
- -Physical examination

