- Hernia (an organ or fatty tissue that squeezes through a weak spot in a surrounding muscle or connective tissue)
- Infection
- Pain
- Angina pectoris (chest pain, pressure or squeezing in the chest)
- Arrhythmia (an unusal rate or rhythm of the heart)
- Atrial fibrillation (irregular and often rapid heart rate)
- Cardiovascular disorder
- Coronary artery disorder
- Abnormal electrocardiogram (unusal test of the electrical activity of the brain)
- Extrasystoles (a premature contraction of the heart)
- Hypotension (low blood pressure)
- Migraine

- Myocardial infarct (heart attack)
- Palpitation (perceived abnormal heart rate)
- Peripheral vascular disorder
- Phlebitis (inflammation of a vein)
- Tachycardia (rapid heart rate)
- Varicose vein
- Vascular disorder (vein disorder)
- Vasodilatation (dilation of the blood vessels)
- Venous thromboembolic events (deep vein thrombosis, pulmonary embolus) (a serious blood clot)
- Chronic indigestion
- Dark urine
- Muscle cramps, pain, stiffness, swelling or weakness
- Trouble breathing
- Unusual bleeding or bruising
- Unusual tiredness
- Yellow eyes or skin

Randomization: Subjects will be assigned to a study group by chance (like a coin flip) rather than by a medical decision made by the researchers. The treatment subjects receive may prove to be less effective or to have more side effects than the other study group(s), or than standard treatments available for subjects' condition.

Placebo: During this study there is a 25% chance that subjects will receive a placebo. This could lengthen the amount of time before subjects receive a treatment that may be effective. During this time, subjects may experience worsening of their condition, including increased HD symptoms. The researchers will carefully monitor subjects' condition. Subjects may of course withdraw from the study at any time.

Blood draw: Removing blood by a needle may cause temporary pain, bruising, bleeding, swelling, dizziness, and on rare instances fainting or infection.

Psychological discomforts: Some of the procedures may cause embarrassment or anxiety, or the questions the researchers ask subjects may be upsetting or make subjects uncomfortable. If subjects do not wish to answer a question, they can skip it and go to the next question. If subjects do not wish to participate you can stop.

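### The adverse events questionnaire has no pre-dose administration in either Table 1, although other text calls for one, so adverse event counts from Month 1 on may include symptoms present before dosing

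*Combined protocol and SAP*

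**What the plan says.** Section 1, item 4 (Adverse Events) says that known fenofibrate side effects will be monitored "using a questionnaire specifically designed for this purpose", together with blood pressure readings and renal and hepatic blood tests, at each monthly visit.

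The schedule is then given in several places:

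- **Table 1, Sections 6.B.1 and 6.C.1.** The row "Adverse events questionnaire" is marked at the six monthly visits only.
- **Procedures paragraph, Sections 6.B.1 and 6.C.1.** "The trial will last 6-months and will require eight study visits". What every visit is to contain includes "medication and medical history update; adverse events questionnaire; study drug accounting and distribution".
- **Baseline Visit list, Section 6.B.1.** It contains "Assess adverse events" and names no instrument.
- **Baseline Visit paragraph, Section 6.C.1.** It mentions no adverse event assessment.
- **Monthly Visits, Section 6.B.1.** "The 6, monthly visits will involve a fasting blood draw, a brief clinical examination and completion of an adverse events questionnaire".
- **Monthly Visits, Section 6.C.1.** It describes instead a "query regarding adverse events by the investigators".

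The Statistical Considerations part of Section 6 contains no adverse event analysis. The documents do not define a treatment-emergent event and give no rule for attributing events to study drug.

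**The concern.** The title and the non-technical summary both name safety as a study aim. A symptom questionnaire shows change on treatment only if the same questions were answered before treatment. If the form is first completed at Month 1, a positive answer may describe something new or something the subject already had.

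The risk list in Section 7.B contains complaints that people often have without the drug, such as headache, back pain, nausea, constipation and unusual tiredness. It also contains "Muscle cramps, pain, stiffness, swelling or weakness", which could plausibly overlap with Huntington's disease itself.

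The plan takes pre-dose values for its other safety measures. Renal and hepatic tests are marked at Screening and Baseline in both tables, vital signs are marked at both visits in the Section 6.B.1 table, and HDL-C is set for Baseline in Section 1, item 4. Of the three monitoring tools named there, only the questionnaire has no pre-dose mark.

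Two things are at stake: the symptom rates reported for each arm, and judgements about individual subjects. The Study Drug paragraph in Section 6.B.1 allows side effects to lead to a dose reduction, and in that decision the other arm gives no help.

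**Working it through.** The plan states no figure on this point, so there is none to reproduce. The check has two parts.

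**1. Visits at which the questionnaire is given**

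| Source | Screening | Baseline | Months 1–6 | Total |
|---|---|---|---|---|
| Table 1, 6.B.1 | no | no | yes | 6 of 8 |
| Table 1, 6.C.1 | no | no | yes | 6 of 8 |
| Procedures text, 6.B.1 and 6.C.1 | yes | yes | yes | 8 of 8 |
| Baseline list, 6.B.1 | – | assessment, instrument not named | – | – |
| Baseline paragraph, 6.C.1 | – | not mentioned | – | – |

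Tables and Procedures text differ at exactly the two visits before dosing.

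**2. What a missing baseline does to the between-arm comparison**

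Inputs from the documents: 20 participants randomised 3:1, so 20 × 3/4 = 15 on fenofibrate and 5 on placebo. Assumption: a given symptom is already present in a proportion p of subjects, equal in expectation in the two arms because allocation is random, and the drug has no effect on it. The documents give no p; the range taken is 20% to 40%.

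- Expected reports: 15p on fenofibrate and 5p on placebo.
- Expected difference in proportions: p − p = 0.
- SD of the difference: √[p(1 − p)(1/15 + 1/5)].

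| p | Expected reports, fenofibrate / placebo | SD of difference |
|---|---|---|
| 0.2 | 3.0 / 1.0 | √(0.16 × 0.2667) = 0.207 |
| 0.3 | 4.5 / 1.5 | √(0.21 × 0.2667) = 0.237 |
| 0.4 | 6.0 / 2.0 | √(0.24 × 0.2667) = 0.253 |

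An exact two-binomial calculation shows how often chance alone produces a sizeable gap. At p = 0.2, an excess of at least 20 points on fenofibrate has probability 0.22, and the same excess on placebo 0.20. At p = 0.3 the figures are 0.25 and 0.24. The noise therefore runs in both directions.

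For comparison, suppose the background were removed completely and only true new events at a rate of 5% to 10% remained. The same formula gives √(0.0475 × 0.2667) = 0.113 and √(0.09 × 0.2667) = 0.155. A baseline answer would reduce the noise but could not make a 15 versus 5 comparison precise.

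**The case against.** The case for treating this as minor has four parts.

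**Loose wording.** The Procedures sentence also places drug distribution at every visit, and neither table marks that at Screening. Both tables, Section 1, item 4 and the Section 6.B.1 Monthly Visits text agree on monthly use, and the unnamed Baseline assessment could coexist with a form that starts at Month 1. This stands in part: the Procedures sentence is weak evidence of intent, and the Baseline item in Section 6.B.1 is the better anchor. The passages still do not tell a site whether to give the form before dosing.

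**Other pre-dose records.** Medical history and general and neurological examinations are taken at Screening. The full UHDRS, the investigator's assessment of predominant symptoms and laboratory tests come at Baseline. A pre-existing movement problem could be checked against these. This also stands in part. None of the UHDRS sections listed is named for pain, gastrointestinal or respiratory complaints, and a history is not an item-by-item answer on the same form.

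**Randomisation and blinding.** Pre-existing symptoms fall in both arms and the expected difference is zero. This stands in full for the between-arm contrast. It does not correct the symptom rate reported on fenofibrate or help with an individual subject.

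**Unknown content.** The questionnaire items are not shown, and no text ties them to the Section 7.B list. Section 1, item 4 names myalgia, blood pressure, hepatic and renal function and photosensitivity, without limiting monitoring to these. This stands: how far the form overlaps with background or disease symptoms is an inference. Nor does any text say that a positive answer alone leads to a dose change.

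**Conclusion.** The schedule conflict is real and appears with both versions of Table 1. Under the tables, an answer at Month 1 has no pre-dose counterpart on the same instrument, and per-arm counts from Month 1 on may include symptoms present before dosing. The result is extra imprecision in a 15 versus 5 comparison and harder attribution within subjects. The size given, an SD of about 21 to 25 percentage points for one symptom, rests on an assumed background prevalence of 20% to 40%; part of it comes from the small placebo arm and would remain with a baseline form.

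Three stronger readings are tempting, and the documents support none of them:

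- A reader might infer that disease symptoms are bound to be counted as drug effects. No attribution or counting rule says so.
- A reader might infer that the safety comparison is biased. Chance imbalance in a randomised, blinded trial is variance, not bias.
- A reader might infer that new symptoms cannot be told from old ones at all. History, examinations and the UHDRS give partial pre-dose information; what is missing is the answer on the same form.

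The primary PGC-1α endpoint is unaffected. The point is modest, but a pre-dose answer that was not collected cannot be recovered once dosing has begun, so it should be settled before the first subject is dosed.

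**What to change.** Reconcile the passages so that they give one schedule:

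- Mark the questionnaire at Baseline, before first dose, in both versions of Table 1.
- Name the questionnaire as the instrument for the adverse event item in the Section 6.B.1 Baseline list, and add the same item to the Section 6.C.1 Baseline paragraph.
- Reword the Procedures sentence in both sections so that it claims for each visit only what the tables mark.
- In the Statistical Considerations part of Section 6, state that an item is reported as treatment-emergent only if it is new or worse than the subject's own Baseline answer, and that counts are shown by arm on that basis.

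The cost is one extra administration of an existing form per randomised subject, 20 in all, at a Baseline visit already planned to take 2 to 3 hours, plus the text edits. No visit, blood sample or laboratory test is added.
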